8.1 Screening

Molecular pre-screening

Not applicable.

Screening

At the enrollment visit the patient will complete a written informed consent. There will be no screening period for this study, this will be referred to as Baseline. Once consented, patients will be evaluated for eligibility via the inclusion and exclusion criteria.

8.1.1 Information to be collected on screening failures

Not applicable.

8.2 Subject demographics/other baseline characteristics

Country specific regulations should be considered for the collection of demographic and baseline characteristics in alignment with CRF

8.3 Efficacy

8.3.1 Efficacy assessments

At every 12 week-visit (\pm 2 weeks), the Investigator is required to confirm that the patient continues to have clinical benefit and may continue receiving study treatment.

8.3.2 Appropriateness of efficacy assessments

Due to the nature of the roll over, only clinical benefit will be assessed.

8.4 Safety

Safety assessments are specified in the assessment schedule, [Table 8-1](#).

For details on AE collection and reporting, refer to AE section.

Safety assessments as specified below must be maintained in source documentation for each patient in the study consisting of case and visit notes (hospital or clinical medical records) as well in the clinical DB according to table 8.1. Letter "D" indicates which safety assessments should be recorded in eCRF and/or vendor DB and letter "S" indicates that the assessments should be recorded in site source patient data.

At baseline visit, the data for all assessments (except Obtain inform consent, Confirmation of Clinical Benefit from Study Treatment, and End of phase disposition) will be taken from the parent study.

8.4.1 Physical Examination

A complete physical examination will include the examination of general appearance, skin, neck (including thyroid), eyes, ears, nose, throat, lungs, heart, abdomen, back, lymph nodes, and extremities, vascular and neurological. If indicated based on medical history and/or symptoms, rectal, external genitalia, breast, and/or pelvic exams may be performed. This will be conducted at visits according to the Assessment schedules.

Significant findings that are present prior to joining this study must be included in the Relevant Medical History/Current Medical Conditions screen on the patient's eCRF. Significant findings made after the start of study drug which meet the definition of an Adverse Event must be recorded on the Adverse Event screen of the patients eCRF.

8.4.2 Body weight and blood pressure

Body weight (to the nearest 0.1 kilogram [kg] in indoor clothing, but without shoes) will be measured. Body weight will be measured at visits according to the Assessment schedules.

After the patient has been sitting for 3 minutes, with back supported and both feet placed on the floor, systolic and diastolic blood pressure will be measured three times using an automated validated device, with an appropriately sized cuff. In case the cuff sizes available are not large enough for the patient's arm circumference, a sphygmomanometer with an appropriately sized cuff may be used.

Blood pressure will be measured at visits according to the Assessment schedules.

Body weight and blood pressure should be recorded in eCRF.

8.4.3 Laboratory evaluations

All laboratory evaluations will be performed using central laboratory according to the Assessment schedule: blood chemistry (Albumin, alkaline phosphatase, total bilirubin, calcium, creatinine, CK, GGT, inorganic phosphorus, lipase, amylase, magnesium, potassium, total protein, AST, ALT, sodium, urea/BUN and uric acid, HbA1c), hematology (Hemoglobin, hematocrit, red blood cell count, white blood cell count with differential, (monocytes, eosinophils, basophils, neutrophils, lymphocytes), and platelet count), testosterone, serum cortisol as clinically indicated, urine free cortisol (two 24-hour urine specimens collected), plasma ACTH, 11-deoxycortisol and 11 deoxycorticosterone.

8.4.4 Electrocardiogram (ECG)

Twelve-lead safety ECGs are collected at the study site using ECG equipment available at the sites. This ECG must be read on site by a qualified physician (e.g., the investigator, or another qualified physician such as a consulting cardiologist) on the day they are collected and recorded in eCRF for each patient.

Only ECGs with clinically significant ("notable") abnormalities should be reported as AE. A "notable abnormality" is defined as:

- QTcF > 480msec with acute cardiovascular risk, as assessed by a consulting cardiologist
- Any QTcF > 500msec, confirmed by a consulting cardiologist

- QTcF increase > 60 msec from baseline.

The frequency of the ECG assessment is provided in [Table 8-1](#).

8.4.5 Pregnancy and assessments of fertility

All pre-menopausal women who are not surgically sterile will have pregnancy testing. Pregnancy test will be performed as detailed in the assessment schedule [Table 8-1](#).

Assessments of Fertility

Medical documentation of oophorectomy, hysterectomy, or tubal ligation must be retained as source documents. Subsequent hormone level assessment to confirm the woman is not of child bearing potential must also be available as source documentation in the following cases:

1. surgical bilateral oophorectomy without a hysterectomy
2. reported 12 months of natural (spontaneous) amenorrhea with an appropriate clinical profile.

In the absence of the above medical documentation, FSH testing is required of any female subject, regardless of reported reproductive/menopausal status at screening/baseline.

8.4.6 Pituitary scan

Pituitary MRI scanning with gadolinium enhancement will be performed every 48 weeks or more frequently if clinically needed at visits according to the assessment schedule provided in [Table 8-1](#) using the local site facility. These will be assessed locally to determine the longest diameter and the tumor volume. For MRI (or CT) images that are not interpretable for tumor volume, the longest dimension (in mm) will be summarized instead. If MRI intravenous contrast is contraindicated for a patient, a non-contrast MRI scan should be performed. If MRI cannot be performed at all then a CT (with i.v. contrast if not contraindicated) may be performed. Digital images are to be kept at the site in the event Recordati requests transfer of the files at a later date. The Pituitary MRI scanning should be recorded in eCRF.

8.4.7 Appropriateness of safety measurements

The safety assessments are standard for this indication/subject population.

8.5 Additional assessments

No additional tests will be performed on subjects entered into this study.

9 Study discontinuation and completion

9.1 Discontinuation

9.1.1 Discontinuation of study treatment

Discontinuation of study treatment for a subject occurs when study treatment is stopped earlier than the protocol planned duration, and can be initiated by either the subject or the investigator.

The investigator must discontinue study treatment for a given subject if, he/she believes that continuation would negatively impact the subject's well-being. Study treatment must be discontinued under the following circumstances:

- Emergence of the following adverse events:
 - Hypertension defined as office mean sitting systolic BP > 180 mmHg or mean sitting diastolic BP > 110 mmHg (confirmed and persistent, persistent is defined as unresolved with osilodrostat dose and/or other concomitant medication changes)
 - Any of the following laboratory abnormalities (confirmed):
 - Hyperkalemia (serum potassium > 6.0 mmol/L).
 - Hypokalemia (serum potassium < 2.8 mmol/L).
 - Any of the following laboratory abnormalities (confirmed and persistent):
 - Hyperkalemia (serum potassium > 5.5 mmol/L).
 - Hypokalemia (serum potassium < 3.0 mmol/L).
 - Hyponatremia (serum potassium < 130 mmol/L).
 - AST or ALT > 3.0 x ULN combined with total bilirubin > 2.0 1 ULN without evidence of cholestasis.
 - QTcF > 500 msec, if confirmed by a cardiologist (see [Section 6.5.1.2](#)),
 - QTcF > 480 msec or QTcF increase is > 60 msec compared to baseline if the investigator determines it is no longer safe for the patient to continue in the study, based on ECGs, cardiac examination, and recommendation from a cardiologist.
 - Pituitary tumor growth, if the tumor is < 2mm from the optic chiasm, or symptoms of actual compression of the optic chiasm emerge (visual field loss, cranial nerve palsies, diplopia) confirmed by MRI of the pituitary.
 - Protocol deviations
 - Lost to follow-up
 - Study terminated by the sponsor
 - Administrative problems
 - Physician decision
 - Subject/guardian withdraw consent
 - Subject has completed treatment based on study duration

When current treatment becomes commercially available in the applicable country, the patient will be withdrawn from the study.

- Pregnancy
- Use of prohibited treatment as per recommendations in the prohibited treatment section
- Any situation in which study participation might result in a safety risk to the subject

If discontinuation of study treatment occurs, the investigator should make a reasonable effort to understand the primary reason for the subject's premature discontinuation of study treatment and record this information.

Subjects who discontinue study treatment or who decide they do not wish to participate in the study further should NOT be considered withdrawn from the study UNLESS they withdraw their consent (see withdraw of informed consent section,). **Where possible, they should return for the assessments indicated** in the assessment schedule. If they fail to return for these assessments for unknown reasons, every effort (e.g. telephone, e-mail, letter) should be made to contact the subject/pre-designated contact as specified in the lost to follow-up section. This contact should preferably be done according to the study visit schedule.

If the subject cannot or is unwilling to attend any visit(s), the site staff should maintain regular telephone contact with the subject, or with a person pre-designated by the subject. This telephone contact should preferably be done according to the study visit schedule.

The investigator must also contact the IRT to register the subject's discontinuation from study treatment.

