4.5 Risks and benefits

There is still an unmet need in the treatment of CD: despite available therapies, a substantial number of subjects do not achieve normalization of cortisol, lose biochemical control over time or present medication-related adverse reactions and may stop treatment because of this.

In order to mitigate the potential risks related to the administration of osilodrostat, some procedures will be taking place:

- The starting dose should be the same as the dose provided in the parent osilodrostat study at the time of transition to the roll-over study. However, the investigator can change the dose based on the subject's response; the maximal dose should not exceed 30 mg b.i.d.
- Subjects will be evaluated by the treating investigator for clinical benefit and safety based on the following assessments:
 - Physical examination (every 12 weeks)
 - Body weight / blood pressure (every 12 weeks), 12-lead safety ECG (every 24 weeks), blood chemistry and hematology (every 24 weeks), 11-deoxycortisol and 11 deoxycorticosterone (every 24 weeks), testosterone (every 24 weeks), Urinary Free Cortisol (UFC) (every 12 weeks), serum cortisol as clinically indicated, plasma ACTH (every 12 weeks) and pituitary MRI (every 48 weeks or more frequently if clinically needed).
- AEs and SAEs will be reported continuously and evaluated by the investigator at each visit.
- Drug administration record for dosing of osilodrostat will be completed at baseline and during treatment visits.
- For females, urinary pregnancy test will be performed at each visit (every 12 weeks) and monthly, at home.
- Upon administration of the last drug dose, discontinuation from the study or study end, the patient will have a follow-up visit 30 days later.
- The protocol provides specific guidance for dose modifications and/or stopping rules, due to osilodrostat-related toxicities. In addition, a safety follow-up for liver toxicity and management of QT prolongation have also been included.

Potential subject benefits

There is an unmet medical need in subjects with CS since this is a rare and serious disease but with limited medical treatment options.

An open label, proof-of-concept, single-arm study (CLCI699C2201, LINC 2) has been conducted to assess the safety and tolerability of osilodrostat in patients with CD after 10 weeks of treatment.

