Known risks of treatment with LCI699 in patients with CS include: QT prolongation, hypocortisolism/adrenal insufficiency, AEs related to the accumulation of precursor molecules, including: increased or decreased blood pressure, hypokalemia or hyperkalemia, hyponatremia, weight gain, edema, and increase in the synthesis of sex steroids (primarily adrenal androgens in women) that may lead to menstrual changes and hirsutism in women and acne in either men or women. Skin rash has been observed. Corticotroph tumor progression, with or without compressive symptoms, is a potential risk.

Neutropenia has been observed in a small number of patients with CD receiving osilodrostat. Preliminary assessment suggests that these events might be associated with cortisol levels that are either below normal or have had a rapid and substantial decline from baseline. In the observed cases, neutropenia rapidly reverses either spontaneously (typically after dose decrease) or with discontinuation of osilodrostat.

In addition, the protocol provides specific guidance for safety follow-up for liver toxicity (increased transaminases, increased total bilirubin) and an algorithm for monitoring and management of QT prolongation.

Conclusion

The treatment of patients with CS still represents a challenge: the available treatments do not lead to biochemical control in quite a large number of patients and many of them lose biochemical control over time.

Therefore there is an unmet medical need to develop new drugs with improved safety, efficacy and a more patient-friendly profile.

Based on current safety and efficacy data of osilodrostat, the overall benefit-risk of trial participation is expected to be positive for all subjects to be enrolled in this study.

5 Population

The investigator or designee must ensure that only patients who meet all the following inclusion and none of the exclusion criteria are offered treatment in the study.

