6.5 Dose modification

6.5.1 Dose modifications

6.5.1.1 Dose modification and dose delay

The osilodrostat dose should be adjusted until normalization of cortisol. The treating physician can increase the dose as needed, up to 30 mg b.i.d.

For subjects who are unable to tolerate the current dose, dose adjustments can be done at investigator's discretion. The guidelines below may be followed:

- If the subject has not reached normalization of cortisol, but does not tolerate the current dose, administration of an intermediate dose (between the current and preceding dose) or repeated administration of the preceding, tolerated dose should be considered.
- If the subject has reached normalization of cortisol, but the current dose is no longer tolerated, an intermediate dose between the current dose and previous dose should be considered.
- If the subject had reached normalization of cortisol, but the current dose is no longer efficacious based on cortisol measurements, dose escalation should resume.

- If the subject has low serum cortisol < LLN, and the patient has signs/symptoms of cortisol-withdrawal syndrome or adrenal insufficiency, a dose reduction of LCI699 should be considered.

Any dose changes must be recorded on the Dosage Administration Record eCRF.

At the time of the next study visit, the patient must:

- Return all unused tablets to the site for drug accountability.
- The IRT system specifies which study drug packs are to be dispensed to the patient. **It is very important** for the site personnel and the subject to be aware that it is possible that more than one tablet strength may be dispensed at the same visit.
- Receive instructions on how to administer the dose and dosing schedule.

Additional dose modifications guidance is summarized in [Table 6-2](#). Deviations to mandatory dose interruptions and/or reductions are not allowed. Permanent treatment discontinuation is mandatory for specific events indicated as such in [Table 6-2](#) or listed in Section [Section 9.1.1](#).

Table 6-2 Dose Modification Guidelines for osilodrostat-suspected toxicities

Toxicity	Suggested Actions

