#### 7.4.2 Laboratory parameters

Laboratory data summaries will include all assessments available for the lab parameters collected no later than 30 days of safety follow-up whichever is later after the last study treatment administration date using data from all sources. All laboratory assessments will be listed and those collected later than 30 days after the last study treatment date will be flagged in the listings.

Grading of laboratory values will be assigned programmatically as per NCI Common Terminology Criteria for Adverse Events (CTCAE) version 4.03 or higher. The calculation of CTCAE grades will be based on the observed laboratory values only, clinical assessments will not be taken into account. CTCAE version 5.0 will be applied and an extract of the tests that can be graded is reported in attachment 8.3.

CTCAE Grade 0 will be assigned for all non-missing values not graded as 1 or higher. Grade 5 will not be used. For laboratory tests that are graded for both low and high values, summaries will be done separately and labeled by direction, e.g., sodium will be summarized as hyponatremia and hypernatremia.

---

Study Code: CLCI699C2X01B

For laboratory tests where grades are not defined by CTCAE, results will be categorized as low/normal/high based on laboratory normal ranges.

For laboratory tests where grades are defined by CTCAE:

- Summary table for AEs of grades 3 or 4
- Shift tables using CTCAE grades to compare baseline to the worst on-treatment value
- Worst post-baseline CTCAE grade (regardless of the baseline status). Each patient will be counted only once for the worst grade observed post-baseline

For laboratory tests where grades are not defined by CTCAE,

- Shift tables using the low/normal/high/ (low and high) classification to compare baseline to the worst on-treatment value

The following listings will be produced for the laboratory data (hematology, and biochemistry):

- Listing of all laboratory data with values flagged to show the corresponding CTC grades the classifications relative to the laboratory reference ranges
- Listing of notable laboratory abnormalities (i.e., CTC grade 3 or 4 laboratory toxicities).

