Definition: A disorder characterized by laboratory test results that indicate a low concentration of magnesium in the blood.					
Hyperkalemia	>ULN - 5.5 mmol/L	>5.5 - 6.0 mmol/L; intervention initiated	>6.0 - 7.0 mmol/L; hospitalization indicated	>7.0 mmol/L; life-threatening consequences	Death

Study Code: CLCI699C2X01B

**Definition:** A disorder characterized by laboratory test results that indicate an elevation in the concentration of potassium in the blood; associated with kidney failure or sometimes with the use of diuretic drugs.

Hypokalemia	<LLN - 3.0 mmol/L	Symptomatic with <LLN - 3.0 mmol/L; intervention indicated	<3.0 - 2.5 mmol/L; hospitalization indicated	<2.5 mmol/L; life-threatening consequences	Death
-------------	-------------------	------------------------------------------------------------	----------------------------------------------	--------------------------------------------	-------

**Definition:** A disorder characterized by laboratory test results that indicate a low concentration of potassium in the blood.

Hypernatremia	>ULN - 150 mmol/L	>150 - 155 mmol/L; intervention initiated	>155 - 160 mmol/L; hospitalization indicated	>160 mmol/L; life-threatening consequences	Death
---------------	-------------------	-------------------------------------------	----------------------------------------------	--------------------------------------------	-------

**Definition:** A disorder characterized by laboratory test results that indicate an elevation in the concentration of sodium in the blood.

Hyponatremia	<LLN - 130 mmol/L	125-129 mmol/L and asymptomatic	125-129 mmol/L symptomatic; 120-124 mmol/L regardless of symptoms	<120 mmol/L; life-threatening consequences	Death
--------------	-------------------	---------------------------------	-------------------------------------------------------------------	--------------------------------------------	-------

**Definition:** A disorder characterized by laboratory test results that indicate a low concentration of sodium in the blood.

Blood bilirubin increased	>ULN - 1.5 x ULN if baseline was normal; > 1.0 - 1.5 x baseline if baseline was abnormal	>1.5 - 3.0 x ULN if baseline was normal; > 1.5 - 3.0 x baseline if baseline was abnormal	>3.0 - 10.0 x ULN if baseline was normal; >3.0 - 10.0 x baseline if baseline was abnormal	>10.0 x ULN if baseline was normal; >10.0 x baseline if baseline was abnormal	-

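### The mandatory hyponatremia stop in Protocol 9.1.1 names potassium instead of sodium; secondarily, the eplerenone rules in 6.2.1.2, Table 6-2 and 6.2.2 disagree

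*Protocol*

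**What the plan says.** Protocol 9.1.1 gives circumstances in which study treatment must be discontinued. One group is headed "Any of the following laboratory abnormalities (confirmed and persistent"), and its last electrolyte item is "Hyponatremia (serum potassium < 130 mmol/L"). Section 6.5.1.1 gives these items their force: "Permanent treatment discontinuation is mandatory for specific events indicated as such in" Table 6-2 or listed in Section 9.1.1.

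Elsewhere the analyte is clear. SAP 7.4.2, on tests graded in both directions, says "sodium will be summarized as hyponatremia and hypernatremia". The hyponatremia row of SAP 8.3 has "125-129 mmol/L and asymptomatic" as grade 2. Protocol 4.5 includes the condition among the known risks of the drug: "hypokalemia or hyperkalemia, hyponatremia, weight gain, edema". Protocol 8.4.3 includes sodium in the central-laboratory chemistry panel: "AST, ALT, sodium, urea/BUN and uric acid, HbA1c".

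On eplerenone, Section 6.2.1.2 permits it to treat or prevent edema or low potassium caused by the study drug. The hypokalemia row of Table 6-2 suggests it, or spironolactone, both to prevent and to treat hypokalemia. Section 6.2.2 prohibits it with two exceptions: acute care after a myocardial infarction, and refractory hypokalemia in a patient who also has hypertension or edema.

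**The concern.** A stopping rule that the protocol makes mandatory should be right as printed. This one is right only after the reader has repaired it, and it concerns a risk that the protocol itself names. A site that wants to confirm the intended limit finds no second statement of it in the protocol.

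The eplerenone texts raise a related problem. Hypokalemia is also a known risk, so an investigator will foreseeably turn to Table 6-2 for advice. Following that advice can put the patient outside 6.2.2, and nothing says which section prevails.

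What is at stake is consistent conduct across sites and, possibly, how protocol deviations are coded. No estimate or test is at stake: the study tests no hypothesis, and its primary analysis is a descriptive summary of AEs and SAEs.

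**Working it through.** No sample size, power or event count bears on this, so the check sets the texts side by side.

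**Step 1: does the number fit potassium?** The potassium stops in 9.1.1 are above 6.0 or below 2.8 mmol/L if confirmed, and above 5.5 or below 3.0 mmol/L if confirmed and persistent. The highest potassium cut in SAP 8.3 is above 7.0 mmol/L (grade 4 hyperkalemia). A limit of 130 mmol/L is far outside that range, so the parenthesis taken alone would be met at any plausible potassium value and could not tell patients apart.

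**Step 2: does the number fit sodium?** SAP 8.3 grades hyponatremia as follows.

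| Serum sodium (mmol/L) | SAP 8.3 grade |
|---|---|
| below LLN, down to 130 | 1 |
| 125 to 129, no symptoms | 2 |
| 125 to 129 with symptoms, or 120 to 124 | 3 |
| below 120 | 4 |

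Read as sodium, a stop below 130 begins where grade 1 ends. The label and the number agree with each other and with the SAP. Only the analyte is wrong.

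**Step 3: is the right limit stated elsewhere in the protocol?** Section 4.5 names the risk without a number. Section 8.4.3 lists the test without a limit. Table 6-2 has rows for hypokalemia and hyperkalemia but none for hyponatremia. The follow-up for QT prolongation in 6.5.1.2 asks for normal electrolytes in general terms. None gives a numeric sodium threshold for action.

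**Step 4: could this be a reading artifact or superseded text?** A whole word has been replaced by another, which text extraction does not plausibly produce. The item stands in the current body of the protocol, not in an amendment summary.

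**Step 5: eplerenone, section by section.**

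| Use | 6.2.1.2 | Table 6-2, hypokalemia row | 6.2.2 |
|---|---|---|---|
| Prevention of hypokalemia | permits | suggests | outside the exceptions |
| Treatment of hypokalemia that is not refractory | permits | suggests | outside the exceptions |
| Drug-related edema without hypokalemia | permits | not addressed | outside the exceptions |
| Refractory hypokalemia with hypertension or edema | permits | suggests | allowed |

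Prevention is the clearest conflict. Section 6.2.2 cannot be read as merely narrowing the permission, because prevention can never amount to refractory hypokalemia, yet two places endorse it. The last row shows that the conflict is partial.

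**Step 6: does prohibited eplerenone use trigger a stop?** Section 9.1.1 lists use of prohibited treatment, but ties it to the recommendations in the prohibited-treatment section. Section 6.2.2 and its subsection recommend discontinuation when a drug with torsades risk is needed long term, and ask the investigator to consider several options, including discontinuation, when glucocorticoids run beyond 4 weeks. They make no such recommendation for eplerenone.

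**The case against.** The strongest reply is that the slip corrects itself. The item is labelled hyponatremia and sits under a heading for confirmed and persistent laboratory abnormalities. A normal potassium is neither, and a limit of 130 is so far from any potassium value that no clinician would apply it. Sites can also act without it: the investigator must stop treatment when continuing would harm the patient, any safety risk is a listed reason to stop, and any AE may justify interruption. All of this stands, and it makes misapplication unlikely.

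It also disposes of a stronger reading that a reader might infer: that every patient has technically met a mandatory stop and belongs in the SAP 6.1 category for patients who met withdrawal criteria but were not withdrawn. The label and list heading rule that out.

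On eplerenone, a reader might infer that following Table 6-2 forces permanent discontinuation. Step 6 shows that the documents do not establish this. Nor is every difference between the sections a contradiction. The edema row of Table 6-2 names only spironolactone, and use after myocardial infarction appears only in 6.2.2; silence in the other places conflicts with nothing.

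A last objection is timing. With 23 patients enrolled by 29 January 2019, first patient first visit was no later than that date. About 5 years from then ends no later than about January 2024, roughly seven months after SAP version 3.2 (26 June 2023). An amendment made that late would govern little treatment time. That bears on the value of amending, not on whether the text is wrong.

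**Conclusion.** The hyponatremia stop is wrong as written and should be fixed. The error is certain on the text; its likely practical effect is small. It is more than a background typo because it is the analyte of a mandatory safety stop for a named risk, with no correct numeric version elsewhere in the protocol. The AE/SAE analysis is unaffected.

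The eplerenone inconsistency is real but partial and secondary. It covers prevention and non-refractory treatment of hypokalemia, and edema alone under 6.2.1.2. Whether a patient treated in line with Table 6-2 would be counted under the SAP 6.1 category for excluded concomitant medication depends on the Study Specification Document, which is not among the documents reviewed. The number of patients affected cannot be derived.

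The conclusion rests on one inference, that sodium is meant. The label, the value 130 and SAP 7.4.2 and 8.3 all support it.

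**What to change.** In Protocol 9.1.1, define the hyponatremia stop as serum sodium below 130 mmol/L and leave it in the confirmed and persistent group. Nothing new has to be measured: sodium is in the central panel, and Section 4.5 schedules "blood chemistry and hematology (every 24 weeks").

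In the same amendment, adopt one eplerenone rule and carry it through 6.2.1.2, the hypokalemia row of Table 6-2 and 6.2.2. The direction is the sponsor's clinical choice: either limit the first two to the exceptions in 6.2.2, or widen those exceptions to cover treatment and prevention of drug-related hypokalemia and edema, with close potassium monitoring. The rule should apply from the amendment's effective date, with earlier conduct judged by the version then in force.

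The cost is a written amendment under Section 14.1, with sponsor and IRB/IEC approval and health authority approval where required. The edits are one word in 9.1.1 and an agreed eplerenone statement. No tests, visits, data items or SAP changes are needed.
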